10.1 Common side effects of Ixabepilone65	
10.2 Common side effects of cetuximab71	1
10.3 Reporting of SAEs73	3
11. Data Management70	6
12. Statistical Design and Analyses70	6

1	I3. Reference/Bibliography	79
	12.3 Interim data analysis	.78
	12.2 Statistical analysis	.77
	12.1 Sample size estimate	.76

1.0 Synopsis:

Ixabepilone and capecitabine combination has demonstrated to be an active regimen in patients with metastatic breast cancer (MBC) after failing an anthracycline and a taxane regimen. Cetuximab is active in tumors that express EGFR with demonstrated activity in head and neck and colorectal tumors. A proportion of breast cancers are known to express EGFR. Cetuximab's mechanism of action suggests the possibility of efficacy in breast cancer patients and several studies show that it may be efficacious in Triple Negative Breast Cancer (TNBC). This study seeks to evaluate Ixabepilone alone or in combination with cetuximab as a possible way to increase antitumor activity.

This is a randomized open-label phase II trial, one hundred sixteen triple negative breast cancer patients will be randomized equally between 1) Ixabepilone or 2) Ixabepilone plus Cetuximab. Randomization will be stratified by disease stage (T1N1-3M0 or T2-4 N0-3M0).

At the baseline all patients will receive a physical assessment, imaging, a blood draw, and a biopsy prior to the start of treatment.

1.1 Primary Objective(s):

To determine the pathologic complete response rate (pCR) (breast and axilla) of Ixabepilone versus Ixabepilone when combined with cetuximab in patients with invasive breast adenocarcinoma T1N1-N3M0 or T2-4 N0-3M0 disease who are Triple negative and who are candidates for preoperative chemotherapy.

1.2 Secondary Objective(s):

To evaluate overall objective response rate in both treatment groups.

To assess safety and toxicity of each regimen.

1.3 Exploratory Objective(s):

To correlate the expression of biomarkers such as PTEN, EGFR and EGFRpathway associated genes (including, but not limited to TGF- α , CRYAB, NRAS, KRAS, AKT3, PTEN, MEK1 and KRAS amplicon genes) with the objective clinical and pathologic response.

For all samples available, the following tests will be conducted:

- Immunohistochemical detection of EGFR, and the PTEN expression in tumor tissue samples. For those EGFR-pathway associated genes (including, but not limited to, TGF-α, CRYAB, NRAS, KRAS, AKT3, PTEN, MEK1 and KRAS amplicon genes) an mRNA-based assay will be used.
- Additional exploratory biomarker analysis may be performed on tumor or blood samples during or following the study. Such exploratory analyses may include assessments of somatic gene mutation, gene/chromosome copy number alteration and gene/protein expression for genes/proteins related to sensitivity or resistance to ixabepilone, other micro-tubule agents and cetuximab. These exploratory biomarkers may include, but are not limited to, beta tubulin isoforms, ABC transporters, TACC3, HCAPG, GTSE1, Kallikreins and gene models associated with ixabepilone response.

These analyses will allow for the correlation of biomarkers expression and response to treatment. Tumor tissue samples will be obtained from the original paraffin blocks or slides containing tumor tissue from the initial diagnostic work-up (see section 7.1).

In addition to the diagnostic core needle biopsy for biomarkers at baseline a second search for the same biomarkers will be done at the time of surgery. The following tests will be conducted (prioritized in the order below):

- EGFR expression by IHC
- PTEN expression by IHC
- Estrogen receptor expression by IHC (at baseline only)

- Progesterone receptor expression by IHC (at baseline only)
- Her2 neu expression by IHC and/or FISH (at baseline only)
- Ki67 (MIB-1) by IHC (at baseline only)
- TGF- α expression by mRNA-based assay
- CRYAB expression by mRNA-based assay
- NRAS expression by mRNA-based assay
- KRAS expression by mRNA-based assay
- AKT3 expression by mRNA-based assay
- MEK1 expression by mRNA-based assay
- KRAS amplicon genes expression by mRNA-based assay
- Beta tubulin isoforms
- ABC transporters
- TACC3
- HCAPG
- GTSE1
- Kallikreins and defined gene models associated with ixabepilone response.
- Additional exploratory biomarkers related to ixabepilone, anti-microtubule and cetuximab sensitivity or resistance

The goal of this clinical research study is to compare the effectiveness of each study group of chemotherapy in triple negative breast cancer patients, and to evaluate the pathologic response rate for each group. We will be collecting tissue from the primary tumor for biomarker testing; the procedure will be done at baseline, and at the time of surgery.

TMHRI Version: 8

2.0 Study Flow chart or Schedule of Events

Procedure	Screening/Baseline Visit	Prior to Each Cycle	End-of- Treatment Visit ^a	Follow-up
Eligibility Assessments				
Obtain Informed Consent	Х			
Confirm Inclusion/Exclusion Criteria Met ^b	Х			
Obtain Medical History	Х			
Safety Assessments				
Karnofsky performance scale ^{a b}	Х	Х	Х	
Record Weight and Height	Х	Х	Х	
Document Vital Signs	Х	Х	Х	
Assess Signs and Symptoms and Adverse Events $^{\rm c,o}$	Х	Х	Х	
Perform Pregnancy Test in WOCBP ^d	Х			
Perform mammogram ^e	Х		Х	
Perform ultrasound of breast and nodal region ^e	Х		Х	
(MRI)*				
Perform Laboratory Tests ^{fghi}	Х	Х	Х	Х
Prepare Paraffin Block/Slides ^j	Х		Х	
Obtain Blood Sample for biomarkers ^k **	Х		Х	
Perform Electrocardiogram	Х		Х	
Perform Echocardiogram ¹	Х			
Efficacy Assessments				
Evaluate Tumor Response RECIST Criteria ^m	Х		Х	
Clinical Drug Supplies				
Premed Before Infusion ⁿ		Х		

TMHRI Version: 8

a. Evaluate subjects who discontinue the protocol for reasons other than disease progression every 4 weeks until progression or until they receive additional anti-cancer therapy.

b. Karnofsky Performance Status of =/> 70% is required for study entry.

c. Document signs and symptoms and adverse events at least every 4 weeks until all study drug-related toxicities resolve, stabilize, return to baseline, or are deemed irreversible.

d. Pregnancy tests (serum or urine) should be performed within 72 hours of study start, or whenever pregnancy is suspected.

e. Mammogram and ultrasound should have been performed any time within 90 days prior to beginning of the study treatment and within 3 to 4 weeks of the neoadjuvant therapy completion before surgery. *MRI (magnetic resonance imaging) should be performed only if requested by the physician.

f. Laboratory tests comprise albumin, alkaline phosphatase, ALT, AST, total bilirubin, blood urea nitrogen, calcium, chloride, creatinine, glucose, lactic dehydrogenase, magnesium (at baseline only for the ixabepilone alone arm), potassium, phosphorus, and sodium, as well as complete blood count (Hemoglobin, Hematocrit, RBC, WBC, Platelets) with differential (Neutrophils, Lymphocytes, Monocytes, Eosinophils, Basophils). CrCL "CrCl = [(140 - age) x IBW] / (Scr x 72) (x 0.85 for females)" before every cycle for patients with an abnormal creatinine.

g. Perform laboratory tests within 72 hours of beginning each cycle. Perform baseline laboratory tests within four (4) weeks before administration of study drug

h. Perform complete blood count (Hemoglobin, Hematocrit, RBC, WBC, Platelets) with differential (Neutrophils, Lymphocytes, Monocytes, Eosinophils, Basophils) at week 1 and week 2 for the first 4 cycles and thereafter at the expected time of nadir (lowest count of any type of blood cell).

i. Laboratory tests comprise of calcium, magnesium, and potassium before every dose of cetuximab therapy and for at least 8 weeks following the completion of cetuximab. Replete electrolytes as necessary.

j. Send tissue slides to the central laboratory (see lab manual). Collected at baseline, and at the time of surgery [UPTEN, EGFR and EGFR-pathway associated genes (TGF-a, CRYAB, NRAS, KRAS, AKT3, PTEN, MEK1 and KRAS amplicon genes). Additional exploratory biomarkers may include (but are not limited to) beta tubulin isoforms, ABC transporters, TACC3, HCAPG, GTSE1, Kallikreins and defined gene models associated with ixabepilone response. Tumor biomarkers will be assessed on a formalin-fixed, paraffin-embedded (TFFPET) tumor sample from a previous biopsy (baseline) and from the surgical specimen. A minimum of 15 slides will be collected at each time.

k. Serum sample for biomarkers expression at baseline, and at the time of surgery. ** Optional (Serum sample for biomarkers expression will be done at later time).
 I. A 12-lead ECG with QT measurement should be performed at screening, at the end of study/early termination, and whenever medically indicated. An Echocardiogram should be performed at screening only and whenever medically indicated.

m. Evaluate tumor response using RECIST criteria before chemotherapy and before surgery (from randomization to disease progression or until surgery).

n. Subjects who are to receive ixabepilone are to be premedicated approximately 1 hour before the infusion with both an oral H1 blocker (diphenhydramine 50 mg or equivalent) and an oral H2 blocker (eg, ranitidine 150-300 mg or cimetidine 300–800 mg or nizatidine 150-300 mg or famotidine 20–40 mg); premedication with steroids is indicated in subjects who developed a hypersensitivity reaction to ixabepilone in previous cycles. Subjects who are to receive cetuximab are to be premedicated with an H1 antagonist (e.g., 50 mg of diphenhydramine IV)

o. Monitor the subject for hypersensitivity reactions during and after all infusions.

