2.3 Cycle 1 Clinic Visit

Following confirmation of eligibility, a blocked randomization will be used to randomize patients to either arm 1 or arm 2. A master sequence of randomization numbers for each arm will be generated (see CA163157 Protocol Manual). Once the subject is randomized, administration of study drug must begin within 72 hours. NOTE: If more than 72 hours have elapsed between the blood sampling for laboratory analysis and administration of ixabepilone or cetuximab, then the analyses must be repeated. (Except for cycle 1 for which baseline labs obtained within 2 weeks are accepted.)

• laboratory tests within 72 hours of beginning each cycle comprise albumin, alkaline phosphatase, ALT, AST, total bilirubin, blood urea nitrogen, calcium, chloride, creatinine, glucose, lactic dehydrogenase, magnesium (at baseline only for the ixabepilone alone arm), potassium, phosphorus, and sodium, as well as complete blood count (Hemoglobin, Hematocrit, RBC, WBC, Platelets) with differential (Neutrophils, Lymphocytes, Monocytes, Eosinophils, Basophils). CrCL "CrCl = [(140 - age) x IBW] / (Scr x 72) (x 0.85 for females)" before every cycle for patients with an abnormal creatinine.

• Laboratory tests comprise of calcium, magnesium, and potassium before every dose of cetuximab therapy (before every cycle for the ixabepilone plus cetuximab arm).

 Perform a physical examination; record weight and height, karnofsky performance scale, document vital signs. Assess signs and symptoms and document baseline adverse events.

• Subjects who are to receive ixabepilone are to be premedicated approximately 1 hour before the infusion with either 1)both an oral H1 blocker (diphenhydramine 50 mg or equivalent) and an oral H2 blocker (eg, ranitidine 150-300 mg or cimetidine 300-800 mg or nizatidine 150-300 mg or famotidine 20-40 mg); or 2) with premedication per institutional standards. Premedication with steroids is indicated in subjects who developed a hypersensitivity reaction to ixabepilone in previous cycles. Subjects who are to receive cetuximab are to be premedicated with an H₁ antagonist (e.g., 50 mg of diphenhydramine IV or

equivalent)

• Infuse ixabepilone or ixabepilone plus cetuximab accordingly with the randomization arm.

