2.3.2 Cycle 2 Pre-Infusion Laboratory Visit

• Within 72 hours before beginning the Cycle 2 infusion, obtain blood sample for analysis of albumin, alkaline phosphatase, ALT, AST, total bilirubin, blood urea nitrogen, calcium, chloride, creatinine, glucose, lactic dehydrogenase, potassium, phosphorus, and sodium, as well as complete blood count (Hemoglobin, Hematocrit, RBC, WBC, Platelets) with differential (Neutrophils, Lymphocytes, Monocytes, Eosinophils, Basophils). CrCL "CrCl = [(140 - age) x IBW] / (Scr x 72) (x 0.85 for females)" before every cycle for patients with an abnormal creatinine.

• Laboratory tests comprise of calcium, magnesium, and potassium before every dose of cetuximab therapy (before every cycle for the ixabepilone plus cetuximab arm).

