Serious infusion reactions, requiring medical intervention and immediate, permanent discontinuation of cetuximab included rapid onset of airway obstruction (bronchospasm, stridor, hoarseness), hypotension, and/or cardiac arrest. Severe (NCI CTC Grade 3 and 4) infusion reactions occurred in 2–5% of 1373 patients in clinical trials, with fatal outcome in 1 patient.

Approximately 90% of severe infusion reactions occurred with the first infusion despite premedication with antihistamines. In patients evaluated during clinical trials, hypomagnesemia occurred in 55% of patients (199/365) receiving cetuximab and was severe (NCI-CTC Grade 3 and 4) in 6–17%. The onset of hypomagnesemia and accompanying electrolyte abnormalities occurred days to months after initiation of cetuximab. Periodically monitor patients for hypomagnesemia, hypocalcemia, and hypokalemia, during and for at least 8 weeks following the completion of cetuximab.

The safety of cetuximab in combination with radiation therapy and cisplatin has not been established. Death and serious cardiotoxicity were observed in a singlearm trial with cetuximab, radiation therapy, and cisplatin (100 mg/m²) in patients with locally advanced SCCHN. Two of 21 patients died, one as a result of pneumonia and one of an unknown cause. Four patients discontinued treatment due to adverse events. Two of these discontinuations were due to cardiac events.

It is not known whether cetuximab, is secreted in human milk since IgG antibodies, such as cetuximab, can be excreted in human milk. Because many drugs are excreted in human milk and because of the potential for serious adverse reactions in nursing infants from cetuximab, a decision should be made whether to discontinue nursing or to discontinue the drug, taking into account the importance of the drug to the mother. If nursing is interrupted, based on the mean half-life of cetuximab, nursing should not be resumed earlier than 60 days following the last dose of cetuximab. ^{45, 50, 51}

Adverse Event (AE) related to the study is defined as any untoward medical occurrence in a patient or clinical investigation subject administered a pharmaceutical product and that does not necessarily have to have a causal relationship with this treatment. An AE can therefore be any unfavorable and unintended sign (including an abnormal laboratory finding), symptom, or disease temporally associated with the use of ixabepilone whether or not considered related to ixabepilone.

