12.2 Statistical analysis

All major treatment comparisons between the two randomized groups in this trial will be performed according to the principle of "intention-to-treat", that is, subjects

CA163-157 Clinical Protocol

will be analyzed according to the treatment arm to which patients were randomized, regardless of compliance to assigned treatment. Summary statistics will be provided for overall response rates and pCR rates by treatment arm. The different rates between treatment arms will be compared by Cochran-Mantel-Haenszel test. . Logistic regression models will be used to assess the association between expression of biomarkers (such as PTEN, EGFR and EGFR-pathway associated genes (including, but not limited to TGF- α , CRYAB, NRAS, KRAS, AKT3, PTEN, MEK1 and KRAS amplicon genes) from the baseline and the overall objective or pathologic response, controlled by treatment arm, age, and disease stage. The unpaired t-test will be applied to compare the difference of expression of biomarkers between the baseline and at surgery in the two arms. Benjamini and Hochberg adjustment will be used to adjust multiple comparisons in expressions of all marks. Safety and toxicity of each regimen will be tabulated by type and grade at the end of chemotherapy. Radiographic efficacy assessment will be performed on all patients at the end of chemotherapy. Statistical significance is defined as 2-tailed p=0.05 level. Stata Version 10 (College Station, TX) will be used for all statistical analyses.

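### Magnesium is scheduled at baseline only in Arm 1 but throughout treatment in Arm 2, so the toxicity table cannot support a between-arm comparison of hypomagnesaemia

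*Combined protocol and SAP*

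**What the plan says.** **Arm 1.** Footnote f to the schedule of events (section 2.0) lists "magnesium (at baseline only for the ixabepilone alone arm", and the Cycle 1 visit text (section 2.3) carries the same restriction: "magnesium (at baseline only for the ixabepilone alone arm), potassium, phosphorus, and sodium". The panel for all patients before cycle 2 (section 2.3.2) runs "calcium, chloride, creatinine, glucose, lactic dehydrogenase, potassium, phosphorus, and sodium", with no magnesium. The panels before cycles 3 and 4 (2.3.3, 2.3.4) and at end of treatment (2.4) also omit it. In those sections magnesium appears only in lines tied to cetuximab.

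**Arm 2.** Footnote i requires "calcium, magnesium, and potassium before every dose of cetuximab therapy and for at least 8 weeks following the completion of cetuximab". Sections 2.4 and 2.6 repeat the post-treatment testing. The cycle visit texts qualify the on-treatment frequency as "before every cycle for the ixabepilone plus cetuximab arm", although cetuximab is given weekly (section 7.2).

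**Both arms.** Section 2.7.1 names magnesium among the baseline chemistries. It then asks for a serum chemistry panel before each later cycle without saying what the panel contains, and it permits extra tests when medically indicated.

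**Use of the data.** Assessing the safety and toxicity of each regimen is a secondary objective (section 1.2). The adverse event definition, which follows section 10.2, includes abnormal laboratory findings. Section 12.2 states: "Safety and toxicity of each regimen will be tabulated by type and grade at the end of chemotherapy". Nothing in section 12 says how to present an analyte that is scheduled in one arm only.

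**The concern.** The arms differ by cetuximab alone, so a reader of the toxicity table will take the difference between columns as the effect of adding cetuximab. For hypomagnesaemia, one column comes from repeated testing and the other from no scheduled post-baseline testing. A low or empty Arm 1 entry would then reflect the test schedule and say little about ixabepilone.

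The event is common by the protocol's own account. Section 10.2 reports that "hypomagnesemia occurred in 55% of patients (199/365) receiving" cetuximab, and that it was severe in 6–17%. A non-zero rate on ixabepilone alone is plausible: section 10.1 lists vomiting and diarrhoea among its common reactions, and hypokalaemia among serious reactions seen with ixabepilone alone or in combination. The documents give no rate.

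The imbalance arises during treatment. Aligning the post-treatment follow-up or the tabulation window would not remove it.

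**Working it through.** **1. Scheduled magnesium tests after baseline**

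| | Arm 1 | Arm 2 |
|---|---|---|
| During treatment | 0 | about 12 by footnote i (4 cycles × 3 weekly doses); 4 by the cycle visit texts |
| After treatment | 0 | at least 8 weeks, frequency not stated |

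The first Arm 2 test may coincide with baseline. Calcium and potassium remain in the per-cycle panel of both arms, so the complete gap is specific to magnesium.

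**2. The protocol's rate, and the expected Arm 2 count**

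- Section 10.2: 199/365 = 54.5%, which rounds to the stated 55%.
- Arm size from section 12.1: 54.
- Any grade: 54 × 0.545 = 29.4. Severe: 54 × 0.06 = 3.2 to 54 × 0.17 = 9.2.
- Precision for Arm 2 alone: 29/54 = 54%, exact 95% interval 40% to 67%.

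The 55% comes from other cetuximab trials, and section 10.2 puts onset at days to months after starting. Applying it to about 12 weeks of treatment is an assumption.

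**3. Size of the bias**

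Let p1 and p2 be the true rates in Arms 1 and 2, and s the share of Arm 1 cases found by unscheduled tests. Take Arm 2 detection as complete.

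- True difference: p2 − p1
- Apparent difference: p2 − s × p1
- Overstatement: (1 − s) × p1, which is p1 when s = 0

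The p1 values below are assumed. The last column is the difference that equal testing would estimate, with p2 = 54.5% and 54 per arm.

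| p1 | Arm 1 cases (54 × p1) | Overstatement, s = 0 | Difference with equal testing (95% CI) |
|---|---|---|---|
| 5% | 2.7 | 5 points | 50 points (35 to 64) |
| 10% | 5.4 | 10 points | 45 points (29 to 60) |
| 20% | 10.8 | 20 points | 35 points (17 to 52) |

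Worked row, p1 = 10%: SE = √(0.545 × 0.455/54 + 0.10 × 0.90/54) = 0.079; 0.445 ± 1.96 × 0.079 = 0.29 to 0.60.

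**4. What an empty Arm 1 cell would seem to say**

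Read as data, 0/54 has an exact 95% upper limit of 1 − 0.025^(1/54) = 6.6%. That limit has no meaning if the 54 patients were not tested.

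**5. Could the imbalance alone produce a difference?**

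This is an illustration, since no such test is planned. Suppose the true rate is the same in both arms and Fisher's exact test is applied (two-sided 0.05, 54 per arm). The table shows how often it would reject.

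| Common true rate | s = 0 | s = 0.25 | s = 1 (equal testing) |
|---|---|---|---|
| 5% | 5% | 3% | 1% |
| 10% | 46% | 19% | 2% |
| 20% | 97% | 56% | 3% |

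**The case against.** The strongest reply is that the extra Arm 2 testing is drug-specific safety surveillance. Section 10.2 calls for it, and it was never meant as a comparative endpoint. The toxicity objective is stated per regimen, the analysis is a tabulation, and the Cochran-Mantel-Haenszel comparison in section 12.2 follows directly on the response rates. This stands as far as it goes: no formal toxicity test is planned. It does not rescue the Arm 1 figure, because Arm 1 is one of the regimens to be assessed.

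Second, section 2.7.1 can be read as putting magnesium in the per-cycle panel for everyone, and it allows medically indicated tests in either arm. A reader might infer from footnote f that Arm 1 must show zero cases; because of those tests, the documents do not support that. But the explicit restriction in footnote f and section 2.3, and the itemised panels in 2.3.2 to 2.3.4 and 2.4, outweigh an unspecified panel. Tests prompted by symptoms would also not give a rate comparable with routine testing. The passages need reconciling.

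Third, no Arm 1 rate is documented, and hypomagnesaemia is absent from the metabolic reactions listed for ixabepilone in section 10.1. The bias could therefore be small beside 55%. That is correct, and it is why the size is given only as a range under assumption.

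Fourth, comparing the arms at common time points is not fully clean. Footnote i provides for electrolyte repletion, so some Arm 2 values at those points may already be corrected, which would shrink the contrast. This stands, and the fix has to allow for it.

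**Conclusion.** The point holds for one laboratory toxicity. If the plan is followed as written, treatment-emergent hypomagnesaemia in Arm 1 cannot be estimated from protocol testing, and the contrast with Arm 2 is tilted against cetuximab. The tilt is at most the true Arm 1 rate: 5 to 20 points, or about 3 to 11 unseen cases, if that rate is 5% to 20%. This assumes 54 patients per arm and near-complete detection in Arm 2. The expected Arm 2 count of about 29 further assumes that the 55% carries over to this trial.

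A reader might conclude that the toxicity objective cannot be answered for this event. The documents do not support that: the objective is per regimen, and the Arm 2 rate can be estimated with an interval of about 40% to 67%. What is lost is the Arm 1 rate and the comparison. A reader might also take hypomagnesaemia to be cetuximab's leading toxicity. Section 10.2 gives higher rates for acneform rash (76–88%), tiredness or weakness (73%) and diarrhoea (72%); *common* is the right word.

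The primary pCR analysis, the sample size and the power are unaffected. The change should be made because a safety table that misleads on a known toxicity can be corrected at little cost.

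**What to change.** 1. In footnote f and section 2.3, delete the parenthesis that limits magnesium to baseline in the ixabepilone-alone arm.
2. Add magnesium to the chemistry panels before cycles 2, 3 and 4 and at end of treatment (2.3.2, 2.3.3, 2.3.4, 2.4) for both arms.
3. In section 2.7.1, state what the per-cycle chemistry panel contains so that it agrees with these lists. Reconcile footnote i (testing tied to each cetuximab dose) with the cycle visit texts (testing tied to each cycle).
4. In section 12.2, tabulate magnesium grades with patients tested as the denominator. Show the arms side by side only at the common time points, report the additional Arm 2 tests separately, and note that repletion in Arm 2 may reduce the contrast.
5. If Arm 1 is to remain untested after baseline, say in section 12.2 that hypomagnesaemia is reported for Arm 2 only and is not compared between arms.

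**Cost.** Steps 1 to 4 add one analyte to blood already drawn in Arm 1: 4 × 54 = 216 assays, plus the wording changes, with no extra visit or blood draw. Step 5 costs one sentence, but leaves the Arm 1 rate unknown.
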